11.3 Treatments

Data for study drug administration (rescue medication) and concomitant therapies will be listed by treatment group and subject.

11.4 Analysis of the primary variable(s)

The primary aim of this study is to assess the efficacy of CJM112 versus placebo on inflammatory facial lesion counts in patients with moderate to severe inflammatory acne. Therefore, a statistical analysis will be performed on the log transformed inflammatory facial lesion count after 12 weeks. Details are provided in [Section 11.4.2](#).

11.4.1 Variable(s)

The primary variable is the natural log transformed total inflammatory facial lesion counts at Week 12.

11.4.2 Statistical model, hypothesis, and method of analysis

The log transformed inflammatory facial lesion count is expected to be approximately normally distributed. It will be analyzed using a Bayesian mixed effect model for repeated measures (MMRM), with log transformed baseline inflammatory facial lesion count as a covariate; treatment sequence, visit, treatment group by visit interaction and log transformed baseline inflammatory facial lesion count by visit interaction as fixed effects. A non-informative prior will be utilized to obtain the posterior estimates. Unstructured covariance structure will be used. Other factors such as gender and race will also be explored for statistical significance if the distribution per factor is reasonably balanced. The log transformed baseline lesion count will be centered and standardized before used in the model.

Data up to Week 12 will be included in the model, for the comparison of CJM112 versus placebo at Week 12, which is of primary interest. Corporate Confidential Information

Bayesian posterior probabilities will be used to assess the following criteria as a guide to decision making ([Fisch et al 2015](#)), though other criteria may be taken into account:

Corporate Confidential Information

The posterior estimates of the treatment effect and the treatment difference (along with its 90% credibility interval) at each visit (with Week 12 being of primary interest) will be provided. The results will be reported in terms of ratio of geometric means by back

transforming the estimates from the log-scale. Data will also be presented in graphics such as spaghetti plot.

11.4.3 Handling of missing values/censoring/discontinuations

All patients with available data after baseline and until Week 12 will be included in the primary analysis. The primary analysis model is known to give unbiased results under the assumption that missing data are at random (MAR), i.e. given observed data the missingness does not depend on unobserved data. If a patient drops out the study according to the predefined discontinuation criteria ([Section 7.2](#)), this MAR assumption remains valid. Besides, last observation carried forward (LOCF) method will be used in a sensitivity analysis to handle missing data.

11.4.4 Sensitivity analyses

A negative binomial or Poisson generalized linear model on facial inflammatory lesion count at Week 12 will be applied as a sensitivity analysis. Baseline lesion count will be used as a covariate and treatment group as a factor.

11.5 Analysis of secondary variable(s)

11.5.1 Safety

Vital signs

All vital signs data will be listed by treatment group, subject, and visit/time and if ranges are available abnormalities (and relevant orthostatic changes) will be flagged. Summary statistics will be provided by treatment and visit/time.

ECG evaluations

All ECG data will be listed by treatment group, subject and visit/time, abnormalities will be flagged. Summary statistics will be provided by period, treatment and visit/time.

Clinical laboratory evaluations

All laboratory data will be listed by treatment group, subject, and visit/time and if normal ranges are available abnormalities will be flagged. Summary statistics will be provided by period, treatment and visit/time.

Adverse Events (AEs)

All information obtained on AEs will be displayed by treatment group and subject.

The number and percentage of subjects with AEs will be tabulated by body system and preferred term with a breakdown by period and treatment. A subject with multiple AEs within a body system is only counted once towards the total of this body system.

Other safety evaluations

Pregnancy test results will be listed by treatment group, subject and visit/time.

Corporate Confidential Information

11.5.2 Pharmacokinetics

Total CJM112 serum concentration data (in microg/mL) will be listed by treatment group, subject, and visit/sampling time point. Descriptive summary statistics will be provided by treatment and visit/sampling time point, including the frequency (n, %) of concentrations below the LLOQ and reported as zero. Summary statistics will include mean (arithmetic and geometric), SD, CV (arithmetic and geometric), median, minimum and maximum. Concentrations below LLOQ will be treated as zero in summary statistics and for PK parameter calculations. A geometric mean will not be reported if the dataset includes zero values.

Pharmacokinetic parameters will be calculated as described in [Section 8.6](#) and will be listed by treatment and subject. Summary statistics will include mean (arithmetic and geometric), SD, CV (arithmetic and geometric), median, minimum and maximum. A geometric mean will not be reported if the dataset includes zero values.

11.5.3 Pharmacokinetic / pharmacodynamic interactions

Not Applicable.

Corporate Confidential Information

Corporate Confidential Information

11.7 Sample size calculation

A total number of 75 patients with a 1:1:1 randomization ratio should provide around 21 patients in each treatment group with complete 12-week data, assuming a dropout rate of around 15%.

Corporate Confidential Information

The 30% difference in total inflammatory facial lesion count at Week 12 between a standard care oral antibiotics and placebo, reported by [Fleischer et al 2006](#), served as reference to define a more stringent threshold of at least 40% difference to placebo for the sample size calculation. Assuming a geometric mean of 20 lesions in the placebo group at Week 12, the 30% difference (a delta of 0.357 on the log scale) corresponds to approximately 6 lesions difference in geometric means; a 40% difference (a delta of 0.511 on the log scale) corresponds to approximately 8 lesions difference in geometric means.

[figure not shown]
Corporate
Confidential
Information

Table 11-1 Operating characteristics of decision rules for n=21 per arm

Sample size	True effect = 0%		True effect = 40%	
	Chance of meeting efficacy criteria (Type I error)	Chance of meeting futility criterion	Chance of meeting efficacy criteria (Power)	Chance of meeting futility criterion (Type II error)
	10+10 (IA1)	5%	40%	77%
21+21 (IA2)	5%	-	90%	-

Note: Calculations assume a SD of 0.47 of log-transformed inflammatory facial lesion count and an effect of 40% over placebo is considered a good effect.

Figure 11-1 Operating characteristics curve for n=21 per arm

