Data analysis	
The log transformed inflammatory facial lesion count will be analyzed using a Bayesian mixed effect model for repeated measures (MMRM), with log transformed baseline inflammatory facial lesion count as a covariate; treatment group, visit, treatment group by visit interaction and log transformed baseline inflammatory facial lesion count by visit interaction as fixed effects and an unstructured covariance structure will be used.
 
Efficacy criteria (only for primary objective) Corporate Confidential Information
 
• If there is at least 90% probability that the treatment effect of CJM112 at Week 12 is better than placebo and• If there is at least 50% probability that the treatment effect at Week 12 is at least 30% (0.357 in the log scale) in favor of CJM112. 
Futility criterion
 
• If there is at least 60% probability that the treatment effect of CJM112 at Week 12 is worse than placebo. 
The posterior estimates of the treatment effect and the treatment difference (along with its 90% credibility interval) at each visit (with Week 12 being of primary interest) will be provided. The results will be reported in terms of ratio of geometric means.
 
Corporate Confidential Information

Key words	Acne, efficacy, safety, PK

1 Introduction

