6.2 Treatment arms

Overall subjects will be assigned to one of the following 3 treatment arms in a ratio of 1:1:1.

Study treatments are defined as:

- CJM112 once monthly for a total of up to 7 doses
- CJM112 once monthly for a total of up to 7 doses
- Placebo for a total of up to 3 doses, followed by re-randomization into either active treatment group for extension period 2 for a total of up to 4 active doses

Both CJM112 and placebo will be provided as liquid in vial according to the dose that is required. Placebo will be matched by volume and number of syringes/injections to maintain double-blind. Details on the study medication preparation will be provided in the Pharmacy Manual provided separately. Dosing is by s.c. administration at time points specified in the [Assessment Schedule](#).

Unbalanced randomization will be used at the start of trial to enhance early comparison of CJM112 vs placebo and interim efficacy/futility assessment. A 3:1:3 randomization

Corporate Confidential Information will be used for the first 35 patients and thereafter 1:2:1 Corporate Confidential Information for the remaining 40 patients. In case more than 75 patients are randomized to the study, the randomization ratio will be 1:1:1 after the first 75 patients.

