10.5 Adjudication Committee

Not required.

11 Data analysis

The analyses will be conducted on all subject data at the time when interim analysis occurs and also when the trial ends. Any data analysis carried out independently by the investigator should be submitted to Novartis before publication or presentation.

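### Does the 21+21 row of Table 11-1 (5% type I error, 90% power) contradict the decision rule it summarises?

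*Protocol*

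**What the plan says.** The Protocol synopsis (Data analysis) sets two efficacy criteria, both required at Week 12: a posterior probability of at least 90% that CJM112 is better than placebo, and of at least 50% that the effect is 30% or more (0.357 on the log scale). Futility is a posterior probability of at least 60% that CJM112 is worse. Protocol Section 11.4.2 specifies a non-informative prior and describes the status of the criteria: "Bayesian posterior probabilities will be used to assess the following criteria as a guide to decision making".

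Section 11.7 then gives "Table 11-1 Operating characteristics of decision rules for n=21 per arm". The legible entries are:

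- **10+10 (IA1):** efficacy 5% and futility 40% under no effect; efficacy 77% under a 40% effect.
- **21+21 (IA2):** efficacy 5% under no effect and 90% under a 40% effect; dashes for futility.

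The note to the table reads: "Calculations assume a SD of 0.47 of log-transformed inflammatory facial lesion count and an effect of 40% over placebo is considered a good effect". The accompanying plot is titled "Figure 11-1 Operating characteristics curve for n=21 per arm".

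On timing, the opening of Section 11 says: "The analyses will be conducted on all subject data at the time when interim analysis occurs and also when the trial ends". Section 6.2 explains that the unbalanced start is meant "to enhance early comparison of CJM112 vs placebo and interim efficacy/futility assessment".

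**The concern.** The table title names 21 per arm and the row is tagged 21+21, so the natural first reading is one analysis at that size. On that reading the row fails. The 30% criterion is a fixed threshold on the estimate, so the chance of crossing it by luck must fall sharply when the sample roughly doubles. The table shows 5% at both sizes.

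If the figures were wrong, the only readable power statement in the protocol would be wrong. The chance of missing a true 40% effect at the 21-per-arm analysis would be about 14% where the table implies 10%.

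A second worry is which active arm the row describes. The 3:1:3 ratio "will be used for the first 35 patients and thereafter 1:2:1". The first 35 patients therefore split 15/5/15, and the arm with 5 patients could not supply a 10+10 comparison from that cohort.

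**Working it through.** **Inputs.** SD 0.47, a 40% effect = 0.511 and a 30% effect = 0.357 on the log scale (Section 11.7); the efficacy and futility criteria (synopsis); a non-informative prior (Section 11.4.2). With a flat prior and known SD, the posterior of the difference is normal around the estimate, with SE = 0.47 × √(2/n).

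**The rule as a cut-off.** The 90% criterion needs an estimate of at least 1.2816 × SE. The 50% criterion needs at least 0.357.

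| n per arm | SE | Cut-off from 90% criterion | Cut-off from 50% criterion |
|---|---|---|---|
| 10 | 0.2102 | 0.269 | 0.357 |
| 21 | 0.1450 | 0.186 | 0.357 |

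The 0.357 cut-off is the binding one at both sizes.

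**IA1 row reproduced (n = 10).**
- No effect: 1 − Φ(0.357/0.2102) = 4.5% (printed 5%).
- 40% effect: Φ((0.511 − 0.357)/0.2102) = 76.8% (printed 77%).
- Futility under no effect: 40% (printed 40%).

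This confirms the rule, the prior and the SD.

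**21+21 as a single look.**
- No effect: 1 − Φ(0.357/0.1450) = 0.7% (printed 5%).
- 40% effect: Φ((0.511 − 0.357)/0.1450) = 85.6% (printed 90%).

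No single SD rescues this reading: 5% would need an SD of about 0.70, and 90% would need about 0.39.

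**21+21 as a pass at either look.** The first 10 per arm are contained in the 21, so the two estimates have correlation √(10/21) = 0.69. The bivariate normal gives:

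| Criteria met | No effect | 40% effect |
|---|---|---|
| IA1 only | 4.06% | 4.7% |
| Both looks | 0.43% | 72.1% |
| IA2 only | 0.27% | 13.5% |
| **Either look** | **4.75%** | **90.3%** |

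These print as 5% and 90%. Four million simulated trials gave 4.76% and 90.3%, and the same figures when the futility criterion stops the trial at IA1.

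**Other readings at 21 per arm that miss the pair** (type I error / power): single look with estimated SD, 0.7% / about 86%; 90% criterion alone, 10% / 98.7%; one-sided 5% test, 5% / 97.0%; criteria required at both looks, 0.4% / 72.1%; pooled doses against placebo, 0.2% / 89.0%; either dose against placebo, 1.3% / 94.6%.

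**The other active arm.** The concern assumes that IA1 uses the first 35 patients. With 15% dropout, each arm with a 3 in the ratio would have 15 × 0.85 = 12.75, about 13 completers. Looks at 13 and 21 give about 2.9% / 89.7%, which does not print as 5% type I error. That assumed timing does not fit the table.

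**The case for a change.** The strongest case for acting is that every number in the concern is right. No legible title, row label or note says that the row is cumulative, and Section 11 foresees an analysis at the interim and another when the trial ends. Under no effect, about 90% of IA1 passes (4.06 of 4.49 points) would not be repeated at 21+21. A reader who carried 90% to the 21-per-arm analysis would be 4.4 points too optimistic, and the repair is a few words.

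The labelling gap stands as far as the readable text goes, but it carries little weight.

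- Text in Section 11.7 directly above the table, the decision criteria text in Section 11.4.2 and other parts of Section 11 are blacked out. These are natural places to define IA1, IA2 and what a pass at each leads to, so the label cannot be called absent from the plan.
- The readable cues favour two looks: the rows are tagged IA1 and IA2, and the title speaks of decision rules in the plural.
- Whether an unrepeated IA1 pass matters depends on what such a pass triggers, which cannot be read. If it triggers the development decision, the cumulative figure is the relevant one.

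The point about the other active arm does not stand. The compared arm is blacked out in Sections 3.2 and 6.2, the interim timing cannot be read, and the one timing assumed for it does not reproduce the table.

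**Conclusion.** The concern does not call for a change. The printed 5% and 90% are correct for a pass at IA1 or IA2 (4.75% and 90.3%), so the two-look design delivers the power it states. The single-look figures at 21 per arm, 0.7% and 85.6%, answer a different question.

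What remains is at most a missing label, which a statistician can recover from the stated inputs in a few lines, as above. Relabelling would alter no sample size, decision rule, analysis or conclusion. Misreading the row has limited consequences: 4.4 points of power, and a type I error that looks larger than it is at the 21-per-arm analysis. The study is described as non-confirmatory, and Section 11.4.2 allows other criteria to be weighed.

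This rests on a normal approximation with known SD 0.47, a flat prior, and nested looks at exactly 10 and 21 per arm. The cumulative reading is inferred from the match to the printed figures. No readable sentence states it.

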11.8 Power for analysis of key secondary variables

Not applicable.

Corporate Confidential Information

12 Ethical considerations

12.1 Regulatory and ethical compliance

This clinical study was designed and shall be implemented, executed and reported in accordance with the ICH Harmonized Tripartite Guidelines for Good Clinical Practice, with applicable local regulations (including European Directive 2001/20/EC, US Code of Federal Regulations Title 21, and Japanese Ministry of Health, Labor, and Welfare), and with the ethical principles laid down in the Declaration of Helsinki.

12.2 Responsibilities of the investigator and IRB/IEC

Before initiating a trial, the investigator/institution must obtain approval/favorable opinion from the IRB/IEC for the trial protocol, written informed consent form, consent form updates, subject recruitment procedures (e.g. advertisements) and any other written information to be provided to subjects. Prior to study start, the investigator is required to sign a protocol signature page confirming his/her agreement to conduct the study in accordance with these documents and all of the instructions and procedures found in this protocol and to give access to all relevant data and records to Novartis monitors, auditors, Novartis Quality Assurance representatives, designated agents of Novartis, IRBs/IECs, and regulatory authorities as required. If an inspection of the clinical site is requested by a regulatory authority, the investigator must inform Novartis immediately that this request has been made.

For multi-center trials, a Coordinating Investigator will be selected by Novartis around the time of Last Patient Last Visit to be a reviewer and signatory for the clinical study report.

12.3 Publication of study protocol and results

The key design elements of this protocol will be posted in a publicly accessible database such as clinicaltrials.gov. In addition, upon study completion and finalization of the study report the results of this trial will be either submitted for publication and/or posted in a publicly accessible database of clinical trial results.

13 Protocol adherence

This protocol defines the study objectives, the study procedures and the data to be collected on study participants. Additional assessments required to ensure safety of subjects should be administered as deemed necessary on a case by case basis. Under no circumstances is an investigator allowed to collect additional data or conduct any additional procedures for any research related purpose involving any investigational drugs under the protocol.

Investigators ascertain they will apply due diligence to avoid protocol deviations. If an investigator feels a protocol deviation would improve the conduct of the study this must be considered a protocol amendment, and unless such an amendment is agreed upon by Novartis and approved by the IRB/IEC and health authorities, where required, it cannot be implemented.

Isolated ALP elevation	
 Repeat liver chemistry tests within 48-72 hours If elevation is confirmed, measure fractionated ALP; if $>50\%$ is of liver origin, establish hepatic causality Complete CRFs per liver event guidance

Criteria	Actions required
Any AE potentially indicative of liver toxicity	
Consider study treatment interruption or discontinuationHospitalize if clinically appropriateComplete CRFs per liver event guidance

Table 15-3 Exclusion of underlying liver disease

Disease	Assessment
Hepatitis A, B, C, E	
IgM anti-HAV; HBSAg, IgM anti-HBc, HBV DNA; anti-HCV, HCV RNA, IgM & IgG anti-HEV, HEV RNA
CMV, HSV, EBV infection	
IgM & IgG anti-CMV, IgM & IgG anti-HSV; IgM & IgG anti-EBV
Autoimmune hepatitis	
ANA & ASMA titers, total IgM, IgG, IgE, IgA
Alcoholic hepatitis	
Ethanol history, γ GT, MCV, CD-transferrin
Nonalcoholic steatohepatitis	
Ultrasound or MRI
Hypoxic/ischemic hepatopathy	
Medical history: acute or chronic CHF, hypotension, hypoxia, hepatic venous occlusion. Ultrasound or MRI.
Biliary tract disease	
Ultrasound or MRI, ERCP as appropriate.
Wilson disease	
Caeruloplasmin
Hemochromatosis	
Ferritin, transferrin
Alpha-1-antitrypsin deficiency	
Alpha-1-antitrypsin

16 Appendix 2: Specific Renal Alert Criteria and Actions

Table 16-1 Specific Renal Alert Criteria and Actions

Criteria	Action required
Serum creatinine (sCr) increase 25 – 49% compared to baseline	
 Consider causes and possible interventions Follow up within 2-5 days
Serum creatinine increase \geq 50%	
 Consider causes and possible interventions Repeat assessment within 24-48h if possible Consider drug interruption or discontinuation unless other causes are diagnosed and corrected Consider hospitalization and specialized treatment
Protein-creatinine or albumin-creatinine ratio increase \geq 2-fold or new onset dipstick proteinuria \geq 1+ or Albumin-creatinine ratio (ACR) \geq 30 mg/g or \geq 3 mg/mmol; or Protein-creatinine ratio (PCR) \geq 150 mg/g or >15 mg/mmol	
 Consider causes and possible interventions Assess serum albumin & serum protein Repeat assessment to confirm Consider drug interruption or discontinuation unless other causes are diagnosed and corrected
New onset glucosuria on urine dipstick (unless related to concomitant treatment, diabetes)	Assess & document: 
 Blood glucose (fasting) Serum creatinine Urine albumin-creatinine ratio
New hematuria on dipstick	Assess & document: 
 Urine sediment microscopy Assess sCr and urine albumin-creatinine ratio Exclude infection, trauma, bleeding from the distal urinary tract/bladder, menstruation Consider bleeding disorder

Additional specialized assessments are available to assess renal function or renal pathology.
(Note: In exceptional cases when a nephrologist considers a renal biopsy, it is strongly recommended to make specimen slides available for evaluation by Novartis to potentially identify project-wide patterns of nephrotoxicity.)

Whenever a renal event is identified, a detailed subject history and examination are indicated to identify, document and potentially eliminate risk factors that may have initiated or contributed to the event:

- Blood pressure assessment (after 5 min rest, with an appropriate cuff size)
- Signs and symptoms such as fever, headache, shortness of breath, back or abdominal pain, dysuria, hematuria, dependent or periorbital edema
- Changes in blood pressure, body weight, fluid intake, voiding pattern, or urine output
- Concomitant events or procedures such as trauma, surgical procedures, cardiac or hepatic failure, contrast media or other known nephrotoxin administration, or other potential causes of renal dysfunction, e.g., dehydration, hemorrhage, tumor lysis

Table 16-2 Follow-up of renal events

Action	Follow up
Assess*, document and record in the Case Report Form (CRF) or via electronic data load. Review and record possible contributing factors to the renal event (co-medications, other co-morbid conditions) and additional diagnostic procedures (MRI etc) in the CRF.	
• Urine dipstick and sediment microscopy• Blood pressure and body weight• Serum creatinine, electrolytes (sodium, potassium, phosphate, calcium), bicarbonate and uric acid• Urine output• Event resolution: (sCr within 10% of baseline or protein-creatinine ratio within 50% of baseline)
Monitor subject regularly (frequency at investigator's discretion) until:	
or
 
• Event stabilization: sCr level with $\pm 10\%$ variability over last 6 months or protein-creatinine ratio stabilization at a new level with $\pm 50\%$ variability over last 6 months.

* Urine osmolality: in the absence of diuretics or chronic kidney disease this can be a very sensitive metric for integrated kidney function that requires excellent tubular function. A high urinary osmolality in the setting of an increase in sCr will point toward a “pre-renal” cause rather than tubular toxicity.
